8.3 Clinical laboratory evaluations

Actual laboratory values will be summarized descriptively by week, by dose group and Total. Change from Baseline to last available visit with laboratory values will be summarized descriptively by dose group and Total. If multiple laboratory assessments are taken at the last visit with available data, the last assessment will be used.

Shift tables that cross-tabulate Baseline (low, normal, high relative to normal range, and missing) by end of trial status will be presented by dose group and Total for each laboratory parameter.

The incidence rate of treatment-emergent markedly abnormal laboratory values (based on Common Terminology Criteria for Adverse Events criteria) will be presented by dose group and Total for hematology and biochemistry laboratory parameters only. See Section 13.1 for markedly abnormal criteria.

All laboratory values will be listed with markedly abnormal laboratory values flagged.

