9.5 Laboratory measurements

Hematology assessments will include the following parameters: red blood cell (RBC) count, hemoglobin, hematocrit, platelets, white blood cell (WBC) count, neutrophils, lymphocytes, monocytes, eosinophils, and basophils.

Clinical chemistry assessments will include the following parameters: Sodium, potassium, total calcium, glucose, creatinine, urea, total protein, albumin, alkaline phosphatase, gamma glutamyl aminotransferase (GGT), aspartate aminotransferase (AST), alanine aminotransferase (ALT), and bilirubin.

For urinalysis, urine protein and blood will be measured by the dipstick method. If positive, microscopic assessments will be done for WBC, RBC, and casts and microbiological culture will be undertaken.

Hematology, clinical chemistry, and urinalysis parameters will be assessed at entry Week 0, every 12 weeks starting at Week 14, and at the Completion/Early Termination (ET) and SFU Visits.

Instructions on blood sample collection, processing, storage, and shipping will be provided in the laboratory manual for this study.

For subjects undergoing reinduction, the parameters ESR, hematocrit, and albumin will be measured at Reinduction Weeks 0, 2, and 4.

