13.3 Planned safety analyses

All safety summaries will be based on the Safety Population as a whole, by treatment group, weight, and age stratum.

Treatment emergent adverse events will be summarized descriptively by primary SOC, high level term, and PT. Additional tables will summarize AEs by severity and relationship to study drug, and separate tables will be generated for AEs leading to withdrawal from the study, SAEs, and deaths. Other AEs of special interest including, but not limited to, infections will also be summarized.

The specific set of AEs reported as injection reactions will also be summarized along with their classification as either injection site reactions or systemic hypersensitivity reactions (the latter being further classified as acute or delayed).

Actual laboratory values and changes from Baseline in laboratory values will be summarized. Shift tables to show the change from Baseline in the absolute values and details of treatment emergent markedly abnormal values (based on Common Terminology Criteria for Adverse Events criteria) will be presented by variable.

Actual vital signs values and change from Baseline in vital signs values will be summarized.

Autoantibody levels will be assessed via the presence or absence of ANA and anti-dsDNA, and data will be summarized.

Extent of exposure to treatment will be presented descriptively.

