13 APPENDICES

13.1 Markedly abnormality criteria for laboratory data

Markedly abnormal laboratory values will be defined as those categorized as Grade 3 or 4 based on the Common Terminology Criteria for Adverse Events v3.0. Definitions of markedly abnormal values using the Grade 3 and Grade 4 cut points are given for hematology in Table 1 and Table 2, respectively. Definitions of markedly abnormal values using the Grade 3 and Grade 4 cut points are given for biochemistry in Table 3 and Table 4, respectively.

Table 1 Definitions of Grade 3 markedly abnormal hematology values

Parameter (units)	Markedly Abnormal Definition	
	Low	High
Hemoglobin (g/L)	<80 - 65	N/A
Platelets (X10E9/L)	<50.0 – 25.0	N/A
White blood cells (X10E9/L)	<2.0 – 1.0	N/A
Neutrophils (X10E9/L)	<1.0 - 0.5	N/A
Lymphocytes (X10E9/L)	<0.5 – 0.2	N/A

N/A=Not Applicable

Table 2 Definitions of Grade 4 markedly abnormal hematology values

Parameter (units)	Markedly Abnormal Definition	
	Low	High
Hemoglobin (g/L)	<65	N/A
Platelets (X10E9/L)	<25.0	N/A
White blood cells (X10E9/L)	<1.0	N/A
Neutrophils (X10E9/L)	<0.5	N/A
Lymphocytes (X10E9/L)	<0.2	N/A

N/A=Not Applicable

Table 3 Definitions of Grade 3 markedly abnormal biochemistry values

Parameter (units)	Markedly Abnormal Definition	
	Low	High
Sodium (mmol/L)	<130 - 120	>155 - 160
Potassium (mmol/L)	<3.0 – 2.5	>6.0 – 7.0
Calcium (mmol/L)	<1.75 – 1.5	>3.1 – 3.4
Glucose (mmol/L)	<2.2 – 1.7	>13.9 – 27.8
Creatinine	N/A	>3.0 – 6.0 x ULN
Albumin (g/L)	<20	N/A

This document is a draft and should not be used to support any marketing authorization application and any extensions or variations thereof.

Alkaline phosphatase	N/A	>5.0 – 20.0 x ULN
Gamma glutamyl transferase	N/A	>5.0 – 20.0 x ULN
Aspartate aminotransferase	N/A	>5.0 – 20.0 x ULN
Alanine aminotransferase	N/A	>5.0 – 20.0 x ULN
Bilirubin	N/A	>3.0 – 10.0 x ULN

N/A=Not Applicable

Table 4 Definitions of Grade 4 markedly abnormal biochemistry values

Parameter (units)	Markedly Abnormal Definition	
	Low	High
Sodium (mmol/L)	<120	>160
Potassium (mmol/L)	<2.5	>7.0
Calcium (mmol/L)	<1.5	>3.4
Glucose (mmol/L)	<1.7	>27.8
Creatinine	N/A	>6.0 x ULN
Albumin (g/L)	N/A	N/A
Alkaline phosphatase	N/A	>20.0 x ULN
Gamma glutamyl transferase	N/A	>20.0 x ULN
Aspartate aminotransferase	N/A	>20.0 x ULN
Alanine aminotransferase	N/A	>20.0 x ULN
Bilirubin	N/A	>10.0 x ULN

N/A=Not Applicable.

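### The only planned laboratory shift runs from Baseline to end of trial, so transient out-of-range values that are sub-Grade 3 or ungraded, and not reported as AEs, are counted in no table

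*SAP*

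**What the plan says.** Protocol 9.5 schedules hematology, chemistry and urinalysis at entry, then "every 12 weeks starting at Week 14, and at the Completion/Early Termination (ET) and SFU Visits". Treatment is open-ended (Protocol 5.1.1: to age 18 or US pediatric approval), and long-term safety is the primary objective (Protocol 3; SAP 2.1.1).

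The laboratory displays in SAP 8.3 are:

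- Actual values: "Actual laboratory values will be summarized descriptively by week, by dose group and Total". Under SAP 3.1 these summaries include the minimum and maximum.
- Change: "Change from Baseline to last available visit with laboratory values will be summarized descriptively by dose group and Total".
- Shift: "Shift tables that cross-tabulate Baseline (low, normal, high relative to normal range, and missing) by end of trial status", for every parameter. No by-visit or worst-value shift is planned, and the SAP does not say which visit supplies the end-of-trial status.
- Markedly abnormal values: a treatment-emergent incidence table that "will be presented by dose group and Total for hematology and biochemistry laboratory parameters only". SAP 13.1 sets the threshold: "Markedly abnormal laboratory values will be defined as those categorized as Grade 3 or 4".
- A listing of all values, in which only the markedly abnormal ones are flagged.

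Protocol 13.3 asks for "Shift tables to show the change from Baseline in the absolute values and details of treatment emergent markedly abnormal values". It fixes no post-baseline time point for the shift.

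**The concern.** The shift table uses one post-baseline value per subject and parameter, however long the subject is treated. A subject normal at Baseline whose neutrophils fall below the normal range, or whose transaminases rise above it, and who has recovered by the end, falls in the normal-to-normal cell. The change-from-Baseline summary has the same limit.

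This holds whichever visit is taken as the end, because any single end value misses what came and went before it. In a study whose main purpose is long-term safety, the categorical laboratory summary would then describe where subjects finished and say little about what happened on treatment.

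**Working it through.** The documents give no figure on this point, so there is none to reproduce. The check has two parts.

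**1. What the other displays leave uncounted**

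| Type of transient value | Where it appears |
|---|---|
| Grade 3 or 4, parameter with a 13.1 criterion | Markedly abnormal table; flagged in listing |
| Any grade, reported as an AE | TEAE tables by SOC and PT, with subject counts (SAP 8.2) |
| Below Grade 3, not reported as an AE | By-week minimum or maximum if it is the group extreme; unflagged in listing; no subject count |
| Parameter with no 13.1 criterion, not reported as an AE | As the row above |

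The third row includes, for example, ALT or AST above the upper limit of normal (ULN) up to 5 x ULN, and neutrophils from 1.0 x10E9/L up to the lower limit of normal.

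For the fourth row, Protocol 9.5 lists 10 hematology and 13 chemistry parameters, 23 in all. SAP 13.1 gives criteria for 5 and 11 of them, 16 in all. The other 23 - 16 = 7 are RBC, hematocrit, monocytes, eosinophils, basophils, urea and total protein. Urinalysis has no criterion, and none of the hematology criteria covers high values.

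**2. Illustration of size**

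Inputs from the documents: n = 16 (SAP 4.4) and the draw schedule (Protocol 9.5). Assumptions: all 16 are normal at Baseline on one parameter; the chance p of an out-of-range value per draw is 2 to 5%; draws are independent; duration is 1, 3 or 5 years.

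Assessments over Y years: k = floor((52Y - 14)/12) + 1 scheduled visits, plus 2 for Completion/ET and SFU.

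- 1 year: floor(38/12) + 1 + 2 = 6
- 3 years: floor(142/12) + 1 + 2 = 14
- 5 years: floor(246/12) + 1 + 2 = 23

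The planned shift uses one of these: 1/6 = 17%, 1/14 = 7%, 1/23 = 4%.

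Expected subjects shifted in the planned table: 16p = 0.3 (p = 2%) to 0.8 (p = 5%), whatever the duration.

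Expected subjects shifted in a worst-value table: 16 x [1 - (1 - p)^k].

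| Duration | k | p = 2% | p = 5% |
|---|---|---|---|
| 1 year | 6 | 16 x 0.114 = 1.8 | 16 x 0.265 = 4.2 |
| 3 years | 14 | 16 x 0.246 = 3.9 | 16 x 0.512 = 8.2 |
| 5 years | 23 | 16 x 0.372 = 5.9 | 16 x 0.693 = 11.1 |

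The SFU draw comes 12 weeks after the last dose. If it does not count as on-treatment, k falls by one and the ranges become 1.5 to 3.6 (16 x [1 - 0.98^5] and 16 x [1 - 0.95^5]), 3.7 to 7.8 (k = 13) and 5.7 to 10.8 (k = 22). The picture is unchanged.

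**The case against.** The strongest reply is that little is truly hidden. Protocol 9.1.1 counts an abnormal laboratory finding as a possible AE, and SAP 8.2 tabulates all TEAEs by subject, non-serious ones included. Neutropenia, thrombocytopenia and leucopenia are AEs of interest (Protocol 9.3). Their stand-alone table takes only serious events, but non-serious ones stay in the all-TEAE tables. By-week summaries show each group's extremes, a DSMB reviews safety laboratory data, and with 16 subjects individual courses can be read from the listing. All of this stands. A reader might infer that transient abnormalities go unreported, or that the shift table is the only subject-level count below Grade 3. The documents support neither.

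A reader might also infer that the planned table looks cleaner as follow-up lengthens. It does not: in the illustration its expected count stays at 16p, and only the distance to the cumulative count grows. Nor does the SAP contradict the Protocol, since Protocol 13.3 leaves the post-baseline time point open.

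Finally, every excursion in the illustration is random by construction. The figures show how many isolated excursions a worst-value table would add, not how many meaningful abnormalities the planned table conceals. That also stands, and with no control group such excursions are hard to interpret.

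What the reply does not remove is the residue in part 1 of the working. Minima and maxima do not link a value to a subject's Baseline or count subjects across visits, and an unflagged listing leaves that count to the reader.

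**Conclusion.** The point holds in a limited form. Transient out-of-range values that were not reported as AEs, and that are either below Grade 3 or in a parameter or direction without a 13.1 criterion, are counted by subject in no table and flagged in no listing.

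For one parameter and 16 subjects normal at Baseline, the worst-value table would show about 2 to 4 subjects at 1 year, 4 to 8 at 3 years and 6 to 11 at 5 years, against 0.3 to 0.8 as planned. These figures rest on the assumed 2 to 5% per draw, independence and the assumed durations. Actual exposure is not given. Planned first visits from July 2010 to June 2012 (Protocol 5.1.2) and SAP approval in February 2018 make follow-up of several years plausible, no more. Correlation within subjects would narrow the gap, and fewer than 16 normal at Baseline would lower the counts.

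This concerns completeness of safety reporting in a small descriptive study. No error rate or sample size is affected. Given the primary objective and the low cost, the change is worth making.

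**What to change.** In SAP 8.3, add for each parameter a shift from Baseline category to the lowest on-treatment value and another to the highest, by dose group and overall. State whether results from unscheduled visits count, and define the on-treatment window so that the place of the SFU draw is clear. Keep the end-of-trial shift as the second table.

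The cost is SAP wording and extra table shells built from data already collected. No Protocol amendment is needed, because "Shift tables to show the change from Baseline in the absolute values" already allows it. The downside is more pages and more isolated chance excursions, across 23 blood parameters and in both directions, that are hard to interpret without a control group. A footnote to the tables should say so.

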8.4 Vital signs, physical findings, and other observations related to safety

8.4.1 Vital signs

Actual vital signs values (systolic blood pressure, diastolic blood pressure, and pulse rate) will be summarized descriptively by week, by dose group and Total. Change from Baseline to last available visit with vital signs values will be summarized descriptively by dose group and Total. If multiple vital sign values are taken at the last visit with available data, the last assessment will be used.

Vital sign values will also be listed.

8.4.2 Height and Weight

Actual height and weight values will be summarized descriptively by week, by dose group and Total. Change from baseline to last available visit with height and weight values will be summarized descriptively by dose group and Total. If multiple height and weight values are taken at the last visit with available data, the last assessment will be used.

Height and weight values will also be listed.

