1 SUMMARY

This is a Phase 2b, open-label, multicenter study to assess the safety of certolizumab pegol (CDP870, CZP) in children and adolescents with active Crohn's disease (CD) who completed C87035 or were terminated from C87035 when the study was stopped by UCB.

C87035 was a Phase 2, open-label, multicenter study to assess the safety, efficacy, pharmacokinetics (PK), and immunogenicity of CZP in children and adolescents ages 6 to 17 with moderately to severely active Crohn's disease. The study was performed as a postapproval commitment following the Food and Drug Administration (FDA) approval of CZP for the treatment of adults with moderately to severely active CD. [REDACTED]

[REDACTED] the decision was made to stop C87035 after determining it was inadequate to address the efficacy of CZP for labeling in pediatric subjects. Subjects ongoing in the study were given the opportunity to enter CR0012 without having completed C87035.

Certolizumab pegol, the investigational medicinal product (IMP) is a humanized antibody fragment antigen binding (Fab'), with specificity for human tumor necrosis factor alpha (TNF), conjugated to polyethylene glycol (PEG). The drug intended for use in this study is the liquid formulation of CZP in a prefilled syringe (PFS).

All subjects who complete Week 62 of C87035 or were terminated from C87035 when the study was stopped by UCB (and completed all assessments required for Week 62/Visit 23 at the time of termination) are eligible to enter this open-label extension study.

Following entry, subjects may continue on the CZP dose they were receiving at the end of C87035 (Low-Dose Group or High-Dose Group [weight adjusted in kg]) every 4 weeks (Q4W). The first clinic visit of this study should coincide with the last visit of C87035 (Week 62/Visit 23). Home administration of CZP by the subject/caregiver/appropriate designee as determined by the Investigator will be permitted following appropriate training at clinic visits. For subjects performing home administration, a phone call to the subject and/or the parents/caregiver will be performed by the Investigator (or designee) every 4 weeks between regular clinic visits. A Safety Follow-Up (SFU) Visit will be conducted 12 weeks after the last dose of study medication.

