5.1.1 Study duration per subject

The maximum study duration of CZP treatment may be until the subject reaches the age of 18 years or CZP is approved for use in the US by pediatric subjects with CD. An SFU visit will be conducted 12 weeks following the last dose of study drug.

The end of the study is defined as the date of the last SFU visit of the last subject in the study.

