Convert height increment during preceding 6 to 12 months into velocity (cm/year) as follows:

$$\frac{\text{Present height} - \text{Height 6-12 months previously}}{\text{Interval (months) between heights}} \times 12 = \text{Height velocity (cm/year)}$$

Using height velocity chart, determine centile for height velocity (see below for a copy).

Height velocity should ideally be plotted according to bone age rather than chronologic age. However, if maturity is appropriate for age (not delayed or advanced) it is reasonable to plot and score height velocity according to chronologic age.

In follow-up visits of short-term clinical trials less than 4 months duration, score height velocity the same as the initial score unless there has been an actual height gain.

Method (b):

If reliable height measurements from 6 to 12 months previously are lacking (often the case with newly diagnosed patients), use any earlier heights to assess previous height centile and compare with current height centile. Score according to degree of decrease in height centile.

Guidelines to calculate and incorporate the results of the Height velocity (cm/year) into the PCDAI

This document cannot be used to support any marketing authorization application and any extensions or variations thereof

REDACTED COPY

Height Velocity Reference Values for Calculating the PCDAI (Males)

Age (years)	Height Velocity in cm per year (Males)		
	Minus 2SD	Minus 1SD	Mean
2.5	5.7	7	8.3
3	5.4	6.6	7.8
3.5	5.1	6.3	7.4
4	4.9	6	7.1
4.5	4.7	5.8	6.8
5	4.6	5.6	6.6
5.5	4.5	5.4	6.4
6	4.3	5.3	6.2
6.5	4.2	5.1	6
7	4.2	5	5.9
7.5	4.1	4.9	5.8
8	3.9	4.8	5.6
8.5	3.8	4.6	5.4
9	3.8	4.5	5.3
9.5	3.7	4.5	5.2
10	3.7	4.4	5.1
10.5	3.7	4.4	5.1
11	3.7	4.4	5.2
11.5	3.8	4.6	5.3
12	4	4.9	5.7
12.5	4.8	5.8	6.7
13	6.2	7.4	8.6
13.5	7.1	8.3	9.5
14	6.1	7.2	8.4
14.5	4.1	5.3	6.5
15	2.4	3.6	4.7
15.5	1.2	2.3	3.3
16	0.4	1.3	2.2
16.5	0.1	0.7	1.5
17	0.1	0.4	0.9
17.5	0.1	0.1	0.5

This document cannot be used to support any marketing authorization application and any extensions or variations thereof

Height Velocity Chart (males)

[figure not shown]

Fig. 4. Height velocity for American boys. Red line, 50th centile for boys 2 SD of tempo early; green line, 50th centile for boys 2 SD of tempo late. Λ and v, The 97th and 3rd centiles for peak velocities of early and late maturers, respectively.

Height Velocity Reference Values for Calculating the PCDAI
(Females)

Age (years)	Height Velocity in cm per year (Females)		
	Minus 2SD	Minus 1SD	Mean

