3.3 Definition of Baseline values

For data which were collected at Week 0 of C87035 and prior to receiving any study treatment, the last nonmissing value collected prior to receiving first dose of study medication of C87035 will be defined as the Baseline value. For data such as Crohn's disease history which was collected only at the Screening Visit of C87035, Baseline will be defined as the Screening Visit of C87035.

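### Raw height and weight change to the last visit is dominated by age, sex and follow-up length in growing children; SAP 8.4.2 should add age- and sex-specific SD scores

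*SAP*

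**What the plan says.** SAP 8.4.2 plans three outputs for height and weight:

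- By-visit values: "Actual height and weight values will be summarized descriptively by week, by dose group and Total".
- One change summary: "Change from baseline to last available visit with height and weight values will be summarized descriptively by dose group and Total".
- A listing of all values.

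SAP 3.3 sets the starting point: "the last nonmissing value collected prior to receiving first dose of study medication of C87035 will be defined as the Baseline value". The change therefore spans the parent study as well as CR0012.

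Protocol 1 describes the parent study's subjects as "children and adolescents ages 6 to 17 with moderately to severely active Crohn's disease". Of follow-up, Protocol 5.1.1 says "The maximum study duration of CZP treatment may be until the subject reaches the age of 18 years", with US paediatric approval as the alternative end point. Time in the parent study also differs, because "Subjects ongoing in the study were given the opportunity to enter CR0012 without having completed C87035".

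For height and weight, the SAP plans no SD score, centile, height velocity, annualized change, or change at a common time point. SAP 8 allows safety summaries to be split by age and weight category, but only where appropriate. Protocol 17.2 contains age- and sex-specific height-velocity tables (mean, minus 1SD, minus 2SD) and calls height velocity the most sensitive growth parameter. The plan uses them only to score one item of the PCDAI total.

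**The concern.** A child's expected gain in height depends strongly on age, sex and elapsed time. A mean of raw gains, each taken over a different interval from a different age, mostly reflects who was enrolled and how long they stayed. It gives no benchmark for normal growth, and it can place a child with impaired growth well above one growing normally.

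This matters because the study's purpose is long-term safety in children, and 8.4.2 is the SAP's only summary of height and weight change. A reader could take a large positive mean as evidence that growth was unaffected. With 16 subjects (SAP 4.4) split into two dose columns, a difference between columns could arise simply from a difference in age, sex or follow-up.

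**Working it through.** The documents state no figure for height or weight change, so there is nothing to reproduce. The check asks what raw gain the protocol's own reference values imply.

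**Inputs.** Half-yearly male velocities in cm/year, from the table in Protocol 17.2:

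- Mean, ages 10 to 15: 5.1, 5.1, 5.2, 5.3, 5.7, 6.7, 8.6, 9.5, 8.4, 6.5, 4.7
- Minus 2SD, ages 10 to 15: 3.7, 3.7, 3.7, 3.8, 4.0, 4.8, 6.2, 7.1, 6.1, 4.1, 2.4
- Mean, ages 15 to 17.5: 4.7, 3.3, 2.2, 1.5, 0.9, 0.5

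**Formula.** Trapezoid rule in half-year steps: gain = 0.5 × [(first + last)/2 + sum of the values between].

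**Different ages and follow-up lengths**

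- Mean velocity, 10 to 15: 0.5 × (4.9 + 61.0) = 32.95 cm
- Minus 2SD throughout, 10 to 15: 0.5 × (3.05 + 43.5) = 23.28 cm
- Mean velocity, 15 to 17.5: 0.5 × (2.6 + 7.9) = 5.25 cm
- Ratio of impaired to normal: 23.28 / 5.25 = 4.4

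**Equal follow-up of 2.5 years**

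- Minus 2SD, 10 to 12.5: 0.5 × (4.25 + 15.2) = 9.73 cm, against 5.25 cm for the boy at mean velocity from 15 to 17.5. Age alone is enough to reverse the order.

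**Same starting age, different follow-up**

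- A boy at mean velocity from age 8 gains 5.4 cm in 1 year, 15.8 cm in 3 years and 28.1 cm in 5 years.

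**How far follow-up could differ.** Protocol 5.1.2 gives first entry as July 2010 and last entry as June 2012. The SAP was approved on 13 February 2018. From 1 July 2010 that leaves 7.6 years, and from 30 June 2012 it leaves 5.6 years. Up to 62 weeks in C87035 (62/52.18 = 1.2 years) comes on top. Reaching age 18 or early withdrawal shortens this, in some subjects to a small fraction. These are calendar limits; the documents do not give any subject's follow-up.

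**Share of the variation.** An illustrative simulation used 16 subjects, ages uniform from 6 to 16.5, half of them male, each with a constant velocity SD score, and follow-up cut at age 18. Female velocity was set to 0 beyond the table. The gain expected from age, sex and follow-up alone explained about 91% of the variance in raw height change when follow-up was 1.2 to 1.7 years, and about 95% when it was 0.5 to 8 years. The squared correlation with the child's own growth score was about 5% to 9%. The age and sex mix is assumed.

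**Weight.** The documents contain no weight reference, so no number can be given. The reasoning is the same.

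**The case against.** The strongest reply has four parts.

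1. **Other outputs exist.** By-week values and full listings are planned, and with 16 subjects each trajectory can be read. This stands as far as it goes, and it rules out the stronger reading that the SAP offers nothing beyond the last-visit change. But the by-week values are still raw and mix ages and sexes, and fewer subjects remain at later visits. They fix time since CR0012 entry, not time since Baseline, because time in C87035 differs. A two-level age split leaves wide variation: the male mean velocity is 9.5 cm/year at 13.5 and 0.9 at 17.
2. **Growth is covered elsewhere.** The PCDAI height item is scored against the velocity tables, and Tanner shifts and bone markers are planned. It would therefore be wrong to say that the reference tables go unused. However, the height item is reported only within the PCDAI total, Tanner stage describes puberty, and bone markers do not measure growth attained.
3. **Height and weight are supplementary.** They are not listed as study variables in Protocol 4 or SAP 2.2, and Protocol 13.3 plans no summary of them. No test or conclusion rests on the table. This stands and limits the weight of the point.
4. **The example is chosen to be stark.** It sets the growth spurt against its end and assumes -2SD velocity throughout. That is fair, which is why the equal-follow-up comparison is also shown. The order still reverses, with a smaller gap.

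**Conclusion.** The point holds as a limitation of a descriptive table. The planned mean of raw change cannot show whether growth was normal, and on the protocol's own male table it can rank a boy at -2SD above a normally growing older boy: 23.3 against 5.25 cm in the example, or 9.7 against 5.25 cm over equal follow-up. The by-week values and listings do not remove the problem.

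This rests on the reference table, on constant velocity bands, and on ages and follow-up that the design permits but the documents do not report. The figures are for height only.

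Two stronger inferences are not supported. One is that the table measures age and follow-up instead of growth: raw change does carry some growth signal, though age, sex and follow-up dominate it. The other is that a safety conclusion, test or decision rule is invalid: none is attached to this table.

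**What to change.** In SAP 8.4.2:

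- Add age- and sex-specific SD scores for height and weight from a named published growth reference.
- Summarize change from Baseline in SD score at common visits (for example yearly) and at the last visit, and show each subject's follow-up length from Baseline.
- Keep the raw values and listings.

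If height velocity is shown as well:

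- Report it in the Protocol 17.2 bands: at or above -1SD, between -1SD and -2SD, at or below -2SD.
- Apply the protocol's rule that post-pubertal patients score 0 points. Use the collected Tanner stage, and state which stage counts as post-pubertal.
- Treat ages beyond the tables (females after 14.5, males after 17.5) as not evaluable.
- Note that chronologic age is used because bone age is not collected. The protocol prefers bone age where maturity is delayed or advanced.

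A continuous score of the form (velocity - mean)/(mean - minus 1SD) should be avoided. For a post-pubertal child with no growth it gives (0 - 2.2)/0.9 = -2.4 for a boy of 16 and (0 - 2.9)/0.7 = -4.1 for a girl of 13.5, although the protocol would score both 0 points. At 17.5 the male -1SD and -2SD values are both 0.1, so zero growth scores only (0 - 0.5)/0.4 = -1.25.

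The cost is SAP wording, an external growth reference and modest programming on data already collected. The downside is that many older subjects, especially girls, will not be evaluable for velocity.
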